3.1.2 Displays of Treatment-Emergent Adverse Events

Analysis set:	Safety analysis set	
Analysis variables:	TEAEs that occur before the start of the study drug for Treatment Period II	
	TEAEs that occur after the start of SYR-472 25 mg tablet	
Categories:	Intensity	[Mild, Moderate, Severe]
	Time of onset (day)	TEAEs that occur before the start of the study drug for Treatment Period II
		[1-28, 29-56, 57-Max]
		[1-14, 15-28, 29-Max]
		TEAEs that occur after the start of SYR-472 25 mg tablet
		[1-84, 85-168, 169-252, 253-336, 337-Max]
		[1-14, 15-28, 29-Max]
	Number of days from the immediate study drug administration (days)	[1, 2, 3, 4, 5, 6, 7, 8-Max]
Analysis methodology:	
The following summaries will be provided for the above analysis variables using frequency distributions by treatment group.
 
In the analysis of TEAEs occurring after the start of SYR-472 25 mg tablet, subjects who received SYR-472 25 mg tablet in the safety analysis set will be included in the analyses and the summaries in the consolidated treatment groups will be also provided concerning (1) and (4).
	

TEAEs will be coded using MedDRA dictionary and will be summarized based on SOC and PT. SOC will be sorted alphabetically and PT will be sorted in decreasing frequency for tables provided by SOC and PT. SOC and PT will be sorted in decreasing frequency for tables provided by SOC only or PT only.

- (1) All TEAEs by SOC and PT
- (2) All TEAEs by SOC
- (3) All TEAEs by PT
- (4) Drug-related TEAEs by SOC and PT
- (5) Intensity of all TEAEs by SOC and PT
- (6) Intensity of drug-related TEAEs by SOC and PT
- (7) TEAEs leading to study drug discontinuation by SOC and PT
- (8) Serious TEAEs by SOC and PT
- (9) All TEAEs by SOC and PT over time
- (10) Number of days from the immediate study drug administration for all TEAEs by SOC and PT
- (11) TEAEs whose incidence summarized by PT is 2% or higher (rounded off to the first decimal place) in either treatment group by SOC and PT
- (12) Intestinal obstruction-related TEAEs by SOC and PT
- (13) Acute pancreatitis-related TEAEs by SOC and PT
- (14) QT/QTc interval prolongation-related TEAEs by SOC and PT
- (15) Hypersensitivity-related TEAEs by SOC and PT
- (16) Cardiovascular TEAEs by SOC and PT
- (17) Pemphigoid TEAEs by SOC and PT
- (18) Renal impairment TEAEs by SOC and PT
- (19) Hypoglycemia-related TEAEs by SOC and PT

The frequency distribution and incidence will be provided according to the rules below:

[Number of subjects]

- In the case of “summaries by SOC and PT, by SOC, and by PT” A subject with multiple occurrences of TEAE within a SOC will be counted only once in that SOC. A subject with multiple occurrences of TEAE within a PT will be counted only once in that PT. Percentages of TEAEs will be based on the number of subjects in the analysis set.
- In the case of “summaries of intensity by SOC and PT”

A subject with multiple occurrences of TEAE within a SOC or a PT will be counted only once for the TEAE with the maximum intensity. Percentages of TEAEs will be based on the number of subjects in the analysis set.

- In the case of “summaries by SOC and PT over time”

A subject with a TEAE that occurs in more than one interval is counted in all the intervals that the TEAE occurs. For each time interval, a subject with multiple occurrences of TEAE within a SOC or a PT will be counted only once in that SOC or PT.

When calculating percentages of TEAEs for each time interval, the number of subjects at risk (i.e., “subjects who either have an exposure in the study or have an occurrence of TEAE, during or after the corresponding time interval”) will be used as the denominator. The number of subjects whose “onset of any one of the TEAEs is within the time interval” will be used as the numerator.

- In the case of “summaries of number of days from the immediate study drug administration” by SOC and PT

A subject with a TEAE that occurs in more than one category of number of days is counted in all the categories that the TEAE occurs. For each category of number of days, a subject with multiple occurrences of TEAE within a SOC or a PT will be counted only once in that SOC or PT. Percentages of TEAEs will be based on the number of subjects in the analysis set.

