6.0 STUDY DESIGN AND DESCRIPTION

6.1 Study Design

This is a phase 3, multicenter, randomized, double-blind, placebo-controlled, parallel-group, comparative study (Treatment Period I) and a phase 3, multicenter, open-label, long-term study (Treatment Period II) using placebo as a control to evaluate the efficacy and safety of SYR-472 when administered orally at a dose of 25 mg once weekly in patients with type 2 diabetes mellitus complicated by severe renal impairment or end-stage renal failure and with inadequate glycemic control despite diet and/or exercise therapy (if any) or despite treatment with 1 antidiabetic drug (Table 6.a) in addition to diet and/or exercise therapy (if any).

Table 6.a Concomitant Antidiabetic Drugs Permitted in the Study

Type	Drug Name (Nonproprietary Name or Class)
Rapid-acting insulin secretagogues	Mitiglinide calcium hydrate, repaglinide
α -glucosidase inhibitors	Acarbose, miglitol, voglibose
Insulin preparations	Mixed, intermediate-acting, or long-acting soluble insulin (40 units/day or less*)

*: For change in the dosing unit of insulin preparations, see 2 (2) in Section 7.3.

[figure not shown]
Subjects who enter the screening period after signing informed consent and are considered eligible according to the inclusion and exclusion criteria will be randomly assigned to either of the SYR-472 25 mg group or placebo group. Subjects who are assigned to the SYR-472 25 mg group in Treatment Period I will continue to be treated with SYR-472 25 mg in Treatment Period II, while those assigned to the placebo group will be switched to SYR-472 25 mg in Treatment Period II.

In Treatment Period I, 1 SYR-472 25 mg tablet or placebo tablet will be orally administered once weekly before breakfast. In Treatment Period II, 1 SYR-472 25 mg tablet will be orally administered once weekly before breakfast.

The study period consists of 6 weeks of screening, 52 weeks of treatment, and 2 weeks of follow-up, a total of 60 weeks. The treatment period consists of Treatment Period I (double-blind) between Week 0 and Week 12 and Treatment Period II (open-label) between Week 12 and Week 52. Subjects will visit the site at the start of the screening period (Week -6), Week -2 of the screening period, end of the screening period (Week 0), Week 2 and Week 4 of the treatment period, and at every 4 weeks until Week 52 of the treatment period, and at the end of the follow-up period (Week 54) (total of 18 visits).

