In Study 101, the elimination half-life (mean) of unchanged SYR-472 following the administration of SYR-472 50 mg under fasted conditions (without breakfast) to patients with severe renal impairment and end-stage renal failure was 88.45 and 107.97 hours, respectively, which were longer than those in matched healthy adults (56.43 and 56.75 hours). Based on these results, the time of assessment at the end of the follow-up period was set at Week 54 by reference to 5 times the elimination half-life (18.4 and 22.5 days, or longer) from the last administration of SYR-472 25 mg tablets (Week 51).

(4) Justification for the primary endpoints

According to “the Guideline for Clinical Evaluation of Hypoglycemic Agents (Revised Draft)” [4], HbA1c should be used as an efficacy endpoint in phase 3 studies in principle. In addition, the safety of the study drug should be used as the primary endpoint in long-term studies. Therefore, HbA1c at the end of Treatment Period I will be evaluated as the efficacy endpoint and AEs throughout the treatment period will be evaluated as the safety endpoint.

(5) Justification for the secondary endpoints

In reference to “the Guideline for Clinical Evaluation of Hypoglycemic Agents (Revised Draft)” [4] and based on the results of clinical studies of SYR-472 conducted so far, HbA1c, fasting blood glucose, and glycoalbumin were set as efficacy endpoints, and vital signs, 12-lead ECG, and clinical laboratory test values were set as safety endpoints to evaluate the efficacy and safety of SYR-472 25 mg.

(6) Justification for the inclusion criteria

See Section 7.1.

(7) Justification for the exclusion criteria

See Section 7.2.

(8) Justification for the excluded medications and other exclusions

See Section 7.3.

(9) Justification for the sample size

See Section 13.3.

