9.3.5 Follow-up

All procedures scheduled for the end of the follow-up period will be performed at the 21st day after the final dose of the study drug (reckoned from the day after the final dose).

For subjects who discontinued study treatment, all procedures scheduled for the end of the follow-up period should be performed wherever possible.

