 - TEAEs that occur before the start of the study drug for Treatment Period II: The analysis will be performed based on the evaluation result entered in the CRF under “Pretreatment Event/Adverse Event (Period 1).”
 - TEAEs that occur after the start of SYR-472 25 mg tablet: The analysis will be performed based on the evaluation results entered in the CRFs under “Pretreatment Event/Adverse Event (Period 1)” and “Pretreatment Event/Adverse Event (Period 2 and thereafter).” If the

evaluation results differ between “Pretreatment Event/Adverse Event (Period 1)” and “Pretreatment Event/Adverse Event (Period 2 and thereafter),” the evaluation result of “Pretreatment Event/Adverse Event (Period 2 and thereafter)” will be preferentially used.

- Time of onset: In the analysis of TEAEs that occur before the start of the study drug for Treatment Period II, the time of onset will be calculated by defining the day of the start of the study drug administration as day 1. In the analysis of TEAEs that occur after the start of SYR-472 25 mg tablet, it will be calculated by defining the day of the start of SYR-472 25 mg tablet as day 1.
- Number of days from the immediate study drug administration: To be calculated by defining the day of the immediate study drug administration as Day 1. If the study drug administration and TEAE occur on the same day, the number of days from the immediate study drug administration will be defined as 1 day.
- Complications of hepatobiliary disorders: Concurrent medical conditions summarized as hepatobiliary disorders by SOC.
- MAV: An abbreviation for markedly abnormal value.
- Overall hypoglycemia: Hypoglycemia reported as “Yes” for hypoglycemic symptoms and asymptomatic hypoglycemia.
- Asymptomatic hypoglycemia: Hypoglycemia with an evaluable self-monitoring blood glucose value (i.e., non-missing and determined to be eligible based on “Handling Rules for Analysis Data”) and a measured concentration of ≤ 70 mg/dL but determined to be not accompanied by symptoms of hypoglycemia at the measurement of that blood glucose value. The presence or absence of asymptomatic hypoglycemia will be determined for each blood glucose value measured.

HANDLING OF TIME WINDOW

For each test, observation, and evaluation items, evaluable data (i.e., non-missing data and data determined to be eligible based on “Handling Rules for Analysis Data”) will be handled according to the following rules.

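### In the SAP's TEAEs-over-time display, the Day 253-336 row is not comparable for the placebo/SYR-472 group, whose completers are observed for only about 43 of those 84 days

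*SAP*

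**What the plan says.** SAP 3.1.2 sorts TEAEs that occur after the start of SYR-472 into the onset intervals "1-84, 85-168, 169-252, 253-336, 337-Max" (days), and display (9) gives them by SOC and PT over time. Under the SAP's definition of time of onset, "it will be calculated by defining the day of the start of SYR-472 25 mg tablet as day 1". The same intervals apply to both groups. The display is by treatment group; for this analysis variable only displays (1) and (4) are also given for the groups combined.

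The counting rule for over-time summaries takes as subjects at risk "subjects who either have an exposure in the study or have an occurrence of TEAE, during or after the corresponding time interval". The numerator is the subjects whose "onset of any one of the TEAEs is within the time interval". Nothing in SAP 3.1.2 weights a partly observed interval, shows observed time or asks for a footnote.

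On the calendar, Protocol 6.1 states that "those assigned to the placebo group will be switched to SYR-472 25 mg in Treatment Period II", and sets "Treatment Period II (open-label) between Week 12 and Week 52". Protocol 6.2 puts the last tablet at Week 51. Protocol 9.3.5 has the follow-up procedures "performed at the 21st day after the final dose of the study drug", and Protocol 10.2.1.1 ends routine AE collection at Visit 18, which is the Week 54 visit.

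**The concern.** The two groups reach the end of the study with different lengths of time on SYR-472: about 52 weeks of dosing in one and about 40 in the other. The placebo/SYR-472 group therefore leaves observation partway through the 253-336 interval. Its completers have all taken a tablet after Day 252, so the rule counts each as one full subject at risk, the same as a subject watched for the whole interval.

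That row would then tend to be lower for this group than its own earlier 84-day rows, and lower than the cell beside it for the SYR-472/SYR-472 group, even with an unchanging event rate and no early withdrawals. AEs are the primary safety endpoint, TEAEs over time is one of the analyses that Protocol 13.1.4 lists for them, and Treatment Period II is there to assess long-term safety. A reader looking for a trend with duration of treatment could take a calendar effect for a falling risk.

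**Working it through.** **Inputs.** Week 12 is scheduled on Study Day 85 and Week 52 on Study Day 365 (SAP, Handling of Time Window), so Study Day = 7 × week + 1. The last dose is at Week 51 (Protocol 6.2). Follow-up is on the 21st day after the final dose (Protocol 9.3.5).

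**Reproducing the plan's own date.** Week 51 is 7 × 51 + 1 = Study Day 358. Adding 21 gives Study Day 379. Week 54 is 7 × 54 + 1 = 379. The stated Week 54 visit is reproduced.

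**Placebo/SYR-472 completers.** SYR-472 day = Study Day − 85 + 1.
- Last dose: 358 − 85 + 1 = Day 274. As a check, 40 weekly doses from Day 1 end on 39 × 7 + 1 = Day 274.
- End of AE collection: 379 − 85 + 1 = Day 295.
- Observed within 253-336: 295 − 253 + 1 = 43 days; 43/84 = 51%.

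**SYR-472/SYR-472 completers.** SYR-472 day equals Study Day, so collection ends on Day 379 and all 84 days of 253-336 are observed. Their open-ended last row holds 379 − 337 + 1 = 43 days.

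**Sensitivity to the start of Treatment Period II.** The visit windows of Protocol Appendix A are not in the text, so the shifts below are assumptions. Collection is held to end on Study Day 379.

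| First SYR-472 tablet (Study Day) | Collection ends (SYR-472 day) | Days observed in 253-336 | Share of 84 |
|---|---|---|---|
| 71 (start of SAP Week 12 window) | 309 | 57 | 68% |
| 78 (one week early) | 302 | 50 | 60% |
| 85 (nominal) | 295 | 43 | 51% |
| 92 (one week late) | 288 | 36 | 43% |
| 98 (end of SAP Week 12 window) | 282 | 30 | 36% |

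Even with a start on Study Day 98 the last dose falls on SYR-472 Day 358 − 98 + 1 = 261, after Day 252. The subject therefore still enters the denominator.

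**Effect on the percentage.** Assume a constant hazard and let p be the incidence over a full 84 days. The cell then shows 1 − (1 − p)^(43/84).

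| p over 84 days | Shown | Shown / p |
|---|---|---|
| 1% | 0.51% | 0.51 |
| 5% | 2.59% | 0.52 |
| 10% | 5.25% | 0.53 |
| 30% | 16.7% | 0.56 |
| 50% | 29.9% | 0.60 |

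For scale, if all 53 planned subjects in the group completed, an event with a 10% 84-day incidence would be expected in 5.3 subjects over a full interval and in about 2.8 over the 43 days.

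**The case against.** The strongest reply is that nothing here is miscalculated. The SAP defines its numerator and denominator, and the percentage is the correct crude proportion under that definition. Days 296-336 on SYR-472 do not exist for this group by design, so there is no observed 84-day figure to set it against; the comparison value is a constant-hazard extrapolation. This stands. A reader might infer that the SAP will report this group's late incidence at half its true value. The documents do not support that. The defect is that the cell cannot be compared with its neighbours, and the ratio of about one half holds only for less common events, a constant hazard and a nominal Week 12 start.

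A second reply is that the shorter exposure is visible elsewhere. SAP 1.3.1 tabulates duration of exposure to SYR-472 by group, with the same first four cut points, and completers in this group will appear there at about 274 days. On schedule, the 337-Max row will also have no placebo/SYR-472 subjects at risk. Both observations are correct and help a careful reader, but neither changes or qualifies the percentages in display (9).

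A third reply is that the documents plan no test or between-group contrast on this display. The randomised comparison of AEs lies in the TEAEs before Treatment Period II, and the SYR-472/SYR-472 group carries the full 253-336 evidence. That limits the consequence to how one row of one descriptive display is read.

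A reader might also see a second error in the 337-Max row, which covers about 43 days for the SYR-472/SYR-472 group. That row is labelled open-ended, so it does not present itself as an 84-day interval.

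**Conclusion.** The point holds as one of comparability. On the nominal schedule, placebo/SYR-472 completers are observed for 43 of the 84 days (51%) in the 253-336 row, yet each counts as one full subject at risk beside a group observed for all 84. The share is 43% to 60% if Treatment Period II is assumed to start a week late or early, and 36% to 68% over the SAP's Week 12 window; a shortfall remains throughout. Under a constant hazard and the nominal start, the percentage is about 51-56% of the full-interval value for 84-day incidences up to 30%, and about 60% at 50%. A late fall in this group can therefore arise from the calendar alone, without any dropout.

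It would be too much to infer that the trial's safety conclusions are biased. The overall TEAE summaries do not use these intervals, and the HbA1c analysis is not involved. This is a cheap improvement to a descriptive display of the primary safety endpoint.

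**What to change.** In SAP 3.1.2, display (9), for TEAEs after the start of SYR-472:

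- For each interval and group, add the observed subject-days, counted from the start of the interval to the earlier of its end and the end of the subject's AE collection.
- Add one defined rate beside the percentage and state which it is: either subjects with a first onset in the interval per 100 subject-days, with time stopped at that onset, or events per 100 subject-days. Dividing subjects with onset by all observed days without stopping time would be neither of these.
- Label or footnote the placebo/SYR-472 cell of the 253-336 row as observed to about Day 295, and state that its percentage is not to be compared with cells covering a full 84 days.
- Leave the 337-Max row as it is, apart from showing its observed time.

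The cost is SAP wording, one or two extra columns and a footnote. The dose and visit dates needed are already collected, and the conduct of the trial does not change.

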3.1.3 Subgroup Analysis of Treatment-Emergent Adverse Events

Analysis set:	Safety analysis set	
Analysis variables:	TEAEs that occur before the start of the study drug for Treatment Period II	
	TEAEs that occur after the start of SYR-472 25 mg tablet	
Stratum:	Age (years)	[Min≤ - <65, 65≤ - ≤Max] [Min≤ - <75, 75≤ - ≤Max]
	Hemodialysis	[Yes (end-stage renal failure), No (severe renal impairment)]
	Complications of hepatobiliary disorders	[Yes, No]

Use of antidiabetic drugs (Week -6) [Yes, No]

Rapid-acting insulin [Yes, No]

secretagogues

α -glucosidase inhibitors [Yes, No]

Insulin preparations [Yes, No]

eGFR (mL/min/1.73 m²) (Week 0) [Min≤ - <15, 15≤ - ≤Max]

Analysis methodology: The following summaries will be provided for the above analysis variables using frequency distributions for each stratum by treatment group for TEAEs occurring before the start of the study drug for Treatment Period II and in the consolidated treatment groups for TEAEs occurring after the start of SYR-472 25 mg tablet.

In the analysis of TEAEs occurring after the start of SYR-472 25 mg tablet, subjects who received SYR-472 25 mg tablet in the safety analysis set will be included in the analyses. TEAEs will be coded using MedDRA dictionary and will be summarized based on SOC and PT. SOC will be sorted alphabetically and PT will be sorted in decreasing frequency.

- (1) All TEAEs by SOC and PT
- (2) Drug-related TEAEs by SOC and PT

The frequency distributions will be provided according to the rules below:

[Number of subjects]

A subject with multiple occurrences of TEAE within a SOC will be counted only once in that SOC. A subject with multiple occurrences of TEAE within a PT will be counted only once in that PT.

3.2 Pretreatment Event

3.2.1 Display of Pretreatment Events

Analysis set: All subjects who signed the informed consent form

Analysis variables: PTE

Analysis methodology: The following summaries will be provided for the above analysis variables using frequency distributions.

PTEs will be coded using MedDRA dictionary and will be summarized based on SOC and PT. SOC will be sorted alphabetically and PT will be sorted in decreasing frequency.

- (1) All PTEs by SOC and PT

(2) Serious PTEs by SOC and PT

The frequency distributions will be provided according to the rules below:

[Number of subjects]

A subject with multiple occurrences of PTE within a SOC will be counted only once in that SOC. A subject with multiple occurrences of PTE within a PT will be counted only once in that PT.

3.3 Clinical Laboratory Evaluations and Other Safety Endpoints

3.3.1 Clinical Laboratory Evaluations

3.3.1.1 Hematology and Serum Chemistry

Analysis set:	Safety analysis set		
Analysis variables:	Hematology		
	Red blood cells	Reticulocytes	White blood cells
	Hemoglobin	Hematocrit	Platelets
	Neutrophils	Lymphocytes	Monocytes
	Eosinophils	Basophils	MCV
	MCH	MCHC	
	Serum chemistry		
	ALT	AST	
	γ-GTP	ALP	
	Total bilirubin	Total protein	
	Albumin	Creatinine	
	Amylase	Lipase	
	Blood urea nitrogen	Uric acid	
	Creatine kinase	LDH	
	Total cholesterol	Triglyceride	
	LDL cholesterol	HDL cholesterol	
	High-sensitivity CRP	K	
	Na	Ca	
	Cl	P	
	Fe	Creatinine clearance	
Categories:	Adjudication results based on the normal reference ranges [Low, Normal, High]		
Visits:	Weeks -6, -2, 0, 2, 4, 8, 12, 16, 20, 24, 28, 32, 36, 40, 44, 48, 52, and		

Analysis methodology: The following analysis will be performed for the above analysis variables except for high-sensitivity CRP and creatinine clearance by treatment group. The following analyses of (1) to (2) will be performed for high-sensitivity CRP and creatinine clearance by treatment group.

When the analysis of MAV is performed, if both “upper” and “lower” criteria in the MAV Criteria are applicable to the same test item, the analysis will be performed for each criterion separately. See Appendix 2 of this SAP for the definitions of test items subject to this analysis and the MAV Criteria.

- (1) Summary statistics for each visit and summary statistics for change from Week 0 at each visit after Treatment Period I
- (2) Case plots
- (3) Shift tables showing adjudication results based on normal reference range at Week 0 and each visit after Treatment Period I
- (4) Frequency distributions for MAV before the start of the study drug administration for Treatment Period II and after the start of SYR-472 25 mg tablet

